10.3.3. Missing data

Analyses using mixed-effects models will give inference that is valid under a missing at random (MAR) assumption. If there is substantial differential dropout between arms then we will apply sensitivity analyses to explore robustness of results to missing not at random (MNAR) mechanisms.

10.3.4. Subgroup Analyses

For the primary outcome we will explore subgroup effects through inclusion of an interaction parameter in the primary analysis model. Variables we will consider are:

- Age
- Prostate size
- Symptoms based on I-PSS
- Flow rate
- Voiding efficiency

Full details of all analyses will be pre-specified in the statistical analysis plan.

10.3.5. Health Economics Analysis

An important part of this study is how these new MITS perform against existing technologies within the NHS, both in clinical efficacy and with regards to their cost and cost-effectiveness to the NHS. The economic evaluation will comprise (1) a within trial analysis (WTA) in the form of a cost utility analysis based on incremental cost per QALY gained at 12 months, using responses to the EQ-5D 5L questionnaire (2) a longer term model extrapolating costs and outcomes over a lifetime time horizon and (3) the assessment of patient preferences in the form of a contingent valuation survey or discrete choice experiment to enable a cost-benefit analysis (CBA) where costs and outcomes are valued in commensurate units. Additional secondary analysis will be conducted to generate cost-effectiveness estimates at two years and three years post-intervention.

Data collection from the trial will estimate the cost of the interventions (micro costed) and subsequent use of health services captured over the duration of the trial using assessment of health utilisation, at baseline, six months-, 12 months-, two- and three-years post-intervention. The perspective taken in

our base-case analysis will be that of the NHS and PSS. However, a broader perspective will also be explored which will include costs borne by participants/families captured via a time and travel questionnaire. The timing of this questionnaire will be set at 12 months only to minimise respondent burden. All relevant costs associated with providing treatment and subsequent management will be measured. Unit costs will be derived using routine data sources [57 - 59] and study specific estimates. Discounting of both costs and outcomes will be applied [35] where appropriate. Data on the cost of the intervention and subsequent use of services will be combined with unit costs to produce a cost for each trial participant. From these a mean cost per patient per intervention will be calculated from an NHS perspective. A mean cost taking into account patient incurred costs will likewise be estimated. This information will then be used to subsequently derive QALYs and ICERs. As per the statistical analysis (Section 10.2.), should recruitment to TURP be considered insufficient, we will consider utilising historical control data from previously conducted randomised controlled trials

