4. TRIAL DESIGN

Multi-arm, multi-centre, open-label, non-inferiority, personalised randomised controlled trial with a six-month internal pilot with defined progression criteria. In total, a minimum of 536 participants will be recruited and followed up for three years post-intervention.

Patients who are willing to receive at least two of the four trial interventions can be randomised among treatments they are willing to receive. There are 11 possible randomisation schemes for patients to choose from. (See section 7.2.) Site staff will be counselled to retain equipoise between all four interventions and should not aim to influence the participants choice for the interventions they are willing to receive. To mitigate against surgeon influence the pattern of participant choice will be monitored across sites.

All sites will offer all interventions. In some sites this may be through the use of a Hub and Spoke model, which functions by allowing patients to access a variety of treatments within their locality but not necessarily in their originating hospital or trust. Where this is the case trial participants may receive their study intervention at another hospital or trust, referred to as a 'Spoke' site. The 'Hub' site will be responsible for organising and conducting all study visits, (apart from the study

intervention as detailed above), collecting all study data, communicating with trial participants and liaising with the site/trust carrying out the study intervention as required.

By the nature of the different delivery of treatments and the need to record treatment-specific operative parameters and resource use, blinding of the participant, surgeon, clinical team, Health Economics and TMG is not possible.

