7.2. Randomisation

7.2.1. Randomisation scheme

There will be 11 randomisation schemes available (six 1:1 options, four 1:1:1 options and one 1:1:1:1 option:

- 1. Prostatic urethral lift (PUL) vs Rezum vs Temporary Implantable Nitinol Device (iTIND) vs TURP
- 2. TURP vs Rezum vs PUL
- 3. TURP vs PUL vs iTIND
- 4. TURP vs Rezum vs iTIND
- 5. PUL vs iTIND vs Rezum
- 6. TURP vs Rezum
- 7. TURP vs PUL
- 8. TURP vs iTIND
- 9. Rezum vs PUL
- 10. Rezum vs iTIND
- 11. PUL vs iTIND

For each scheme, randomisation will be performed using permuted random blocks of variable length.

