10.1. Analysis Populations

The following analysis populations are defined for the purpose of analysis:

Analysis Population	Description			
Intention-to-treat (ITT)	Includes all randomised participants, analysed according to			
	randomised treatment allocation.			
Modified intention-to-treat	Includes all randomised participants, continuing to meet the			
	eligibility criteria at the time of intervention, analysed according to			
	randomised treatment allocation.			
Per-protocol	Includes all randomised participants receiving their allocated			
	intervention and continuing to meet the eligibility criteria at the time			
	of intervention, analysed according to randomised treatment			
	allocation.			
As-treated	Includes all randomised participants receiving one of the trial			
	interventions and continuing to meet the eligibility criteria at the			
	time of intervention, analysed according to treatment received.			
Safety	Includes all randomised participants receiving a trial intervention,			
	analysed according to the intervention received.			

For the main analysis of efficacy outcomes, participants will be analysed according to their randomised treatment allocation; whereas safety data and post-operative complications will be reported and analysed according to the intervention they actually received.

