10.2. Sample Size Calculations

The primary outcome is the change in I-PSS total score between baseline and 12 months. The trial is powered to test the non-inferiority (NI) of each experimental arm to the TURP arm in terms of I-PSS. The three null hypotheses to be tested are:

- The mean difference in 12-month I-PSS total score (adjusted for baseline) between PUL and TURP is > 3
- ii. The mean difference in 12-month I-PSS total score (adjusted for baseline) between Rezum and TURP is > 3
- iii. The mean difference in 12-month I-PSS total score (adjusted for baseline) between iTIND and TURP is > 3

To test each hypothesis, participants will be pooled across the following randomisation schemes:

i. TURP vs PUL ii. TURP vs Rezum		iii. TURP vs iTIND
TURP: PUL: Rezum: iTIND	TURP: PUL: Rezum: iTIND	TURP: PUL: Rezum: iTIND
TURP: PUL: Rezum	TURP: PUL: Rezum	TURP: PUL: iTIND
TURP: PUL: iTIND	TURP: Rezum: iTIND	TURP: Rezum: iTIND
TURP: PUL	TURP: Rezum	TURP: iTIND

In data from the UNBLOCS trial (NIHR HTA 12-35-15) [33] the standard deviation (SD) of the I-PSS score at 12-months follow-up was 6.3 (based on the non-catheterised participants with complete data).

A non-inferiority margin of three points is used. This represents the minimally clinically important difference (MCID) for the outcome. [4,46,47] The non-inferiority hypothesis is equivalent to ruling out TURP providing an improvement of the MCID or greater against a minimally invasive treatment.

Assuming a minimally invasive arm has the same mean I-PSS as TURP, standard non-inferiority sample size formula suggests we would require 12-month information on 100 participants per intervention for each comparison for 90% power to conclude non-inferiority at a one-sided type I error rate of 0.0195 (nQuery). This p-value threshold yields a maximum chance of falsely concluding non-inferiority of 5% assuming a Dunnett correction.

We have inflated this sample size to account for a 25% attrition rate, which was seen in UNBLOCS for patient-reported outcomes. This gives a sample size of 134 participants per intervention for each comparison. Since we are adjusting for baseline I-PSS, we would expect power to be higher than 90%.

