10.3.2. Analysis of the Secondary Outcome Measures

Secondary efficacy outcomes will be analysed for superiority of each experimental treatment against control. For each pairwise comparison data will be pooled across randomisation schemes as shown in Section 10.2. Estimated differences between treatment groups will be reported with 95% confidence intervals and two-sided p-values. Analyses will primarily be performed in the per-protocol population (with IPW used where required). Analyses may also be repeated using alternative analysis populations.

Secondary patient-reported outcome measures (including ICIQ-MLUTS — voiding score and incontinence score, ICIQ-MLUTSsex total score, ICIQ-LUTSqol total score, I-PSS-QOL score) up to three years will be analysed using similar linear mixed-effects regression models as described above for the primary outcome measure, but with the baseline value corresponding to the relevant questionnaire included as a fixed effect rather than the baseline I-PSS. Additional scores or items from patient-reported outcome measures may also be reported and analysed using suitable mixed-effects regression models.

Bladder voiding efficiency (BVE) and maximum flow rate (Qmax) at 12 months will be analysed using a linear mixed-effects models, including site as a random effect (this will be the Hub where a Hub and Spoke model is used) and treatment group, randomisation scheme, and baseline measures of the outcome variable of interest as fixed effects.

Length of hospital stay will also be analysed using a linear mixed-effects models, including site as a random effect and treatment group and other stratification factors as fixed effects.

Duration of perioperative catheterisation will be measured as the time from intervention to stopping catheter use. Where a catheter is not required this will be set to zero. Data will be analysed using either a Cox proportional hazards or linear regression model with mixed-effects (including site as a random effect and treatment group and randomisation scheme as fixed effects), depending on whether any censoring is present.

The proportion of participants requiring a blood transfusion will be analysed using a mixed-effects logistic regression model, including site as a random effect and treatment group and randomisation scheme as fixed effects.

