10.3.6. The Within Trial Analysis (WTA)

The base case within trial analysis will compare changes in health-related QoL, based on responses to the EQ-5D-5L at baseline, six weeks, six and 12 months. Responses to the EQ-5D-5L will be combined with a UK tariff that is relevant at the time the study reports and used to estimate QALYs. The results of the analyses will be presented as point estimates of mean incremental costs and QALYs. An adjusted analysis will be used to estimate the point estimates of the mean incremental costs, effects and cost-effectiveness using seemingly unrelated regression (SUR). We will explore the uncertainty in estimates of cost-effectiveness through a stochastic sensitivity analysis drawing bootstrapped samples of mean costs and mean QALYs. Results from this analysis will be combined willingness-to-pay (WTP) threshold values generating cost effectiveness acceptability curves (CEACs) that represent the probability of the interventions being cost-effective at each WTP value. As part of the CEA we will also estimate the distribution of costs and health benefits (QALY gains) by socio-economic status using IMD data.

Secondary analysis will be conducted and the cost-effectiveness analysis will be replicated at two and three years post-intervention.

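### As written, the economic analysis has no randomisation-scheme restriction or scheme term, so treatment preference can confound the ICERs and CEACs

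*Protocol*

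**What the plan says.** **Design.** Protocol section 4: "Patients who are willing to receive at least two of the four trial interventions can be randomised among treatments they are willing to receive". Section 7.2.1 lists 11 schemes with equal allocation inside each: "six 1:1 options, four 1:1:1 options and one 1:1:1:1 option". Four contain no TURP arm: the three-way scheme "5. PUL vs iTIND vs Rezum" and the two-way schemes 9, 10 and 11.

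**Clinical outcomes.** Section 10.2: "To test each hypothesis, participants will be pooled across the following randomisation schemes". The table that follows gives four schemes per comparison, each containing both TURP and the MIT in question. Section 10.3.1 uses these sets for the primary analysis, with scheme as a fixed effect. Section 10.3.2 does the same for secondary efficacy outcomes: "For each pairwise comparison data will be pooled across randomisation schemes as shown in Section 10.2". Most of its models name scheme as a fixed effect. Section 10.3.1 also pools all 11 schemes, but only as a supplementary analysis and with weighting or a similar method to deal with patient differences between arms.

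**Economic outcomes.** Cost per QALY at 12 months and the CEACs are the primary economic outcomes (section 3). Section 10.3.5 builds a cost for every man and continues: "From these a mean cost per patient per intervention will be calculated from an NHS perspective". It says this information feeds the ICERs. Section 10.3.6: "An adjusted analysis will be used to estimate the point estimates of the mean incremental costs, effects and cost-effectiveness using seemingly unrelated regression (SUR"). Uncertainty comes from bootstrapped mean costs and mean QALYs. Sections 10.3.5 to 10.3.8 do not mention randomisation scheme.

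**The concern.** Under personalised randomisation, which scheme a man enters is his own choice. Chance decides his arm only within that scheme. A mean over all men who share an arm therefore mixes the effect of allocation with the characteristics of men who chose schemes containing that arm.

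The mixing runs both ways. Each MIT arm includes men who were not willing to have TURP. The TURP arm includes men who were not willing to have the particular MIT. If these groups differ in baseline utility, comorbidity or service use, the difference enters incremental costs and QALYs as though treatment had caused it, and passes into the ICERs and CEACs.

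The protocol recognises the problem for I-PSS, where it allows all-scheme pooling only as a supplementary analysis with a correction. The primary economic comparison carries neither safeguard in the text. The pooling rule in section 10.3.2 is written for secondary efficacy outcomes and does not reach costs or QALYs.

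**Working it through.** **1. The plan's own figure.** Section 10.2 gives SD 6.3, margin 3, one-sided alpha 0.0195, power 90% and attrition 25%.

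- n per arm = 2 × 6.3² × (2.064 + 1.282)² / 3² ≈ 98.7, so 99 by the normal approximation. The noncentral t gives 90.06% power at n = 100, as stated.
- 100 / 0.75 = 133.3, so 134; 4 × 134 = 536.

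The sample size reproduces and is not affected by this point. N = 536 is used below only for scale.

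**2. Arm composition under equal uptake (assumed).** Each scheme of size k sends 1/k of its men to each arm. For PUL:

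- All schemes containing PUL (1, 2, 3, 5, 7, 9, 11): 1/4 + 3 × 1/3 + 3 × 1/2 = 2.75.
- Of these, without TURP (5, 9, 11): 1/3 + 1/2 + 1/2 = 1.333.
- Share of the PUL arm from no-TURP schemes: 1.333 / 2.75 = 48.5%.

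Rezum and iTIND give the same by symmetry. For the TURP arm, the schemes without PUL (4, 6, 8) also sum to 1.333 of 2.75, again 48.5%.

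At N = 536 there are 536 / 11 = 48.7 men per scheme. Each arm has 2.75 × 48.7 = 134 men, of whom 1.417 × 48.7 = 69 come from schemes shared with the comparator and 65 do not.

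**3. Range over uptake.** The protocol gives no uptake figures. Let q be the proportion of men choosing a no-TURP scheme, spread evenly over those four, with 1 − q spread evenly over the other seven. Then

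share of MIT arm = (1.333 q/4) / [1.333 q/4 + 1.417 (1 − q)/7].

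| q | MIT arm from no-TURP schemes | Men per arm in shared schemes, N = 536 |
|---|---|---|
| 0% | 0% | 108 |
| 10% | 15.5% | 98 |
| 20% | 29.2% | 87 |
| 36% (equal uptake) | 48.5% | 69 |
| 50% | 62.2% | 54 |

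Under this even spread, the share of the TURP arm from schemes without the given MIT stays at 48.5% in every row. Even at q = 0 the mixing is therefore not removed.

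**4. From composition to bias.** Allocation is equal within each scheme, so the four shared schemes contribute equally in expectation to both arms and their pooled contrast is balanced. The bias in an unadjusted all-scheme MIT-minus-TURP mean is therefore

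bias = s_M × d_M − s_T × d_T,

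where s_M and s_T are the shares of the MIT and TURP arms from outside the shared schemes, and d_M and d_T are the mean differences, within each arm, between those men and men in the shared schemes. The documents give neither d_M nor d_T. The two terms can offset or reinforce each other, so neither size nor direction can be stated.

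**The case against.** The strongest reply is that the economic section is silent rather than wrong. The increments come from the SUR, which is described as adjusted. Its covariates are not named, and scheme could be one. Covariate lists and bootstrap strata often belong in an analysis plan, and none is shown here. This reply stands in part. A reader might infer that the economic comparison is no longer randomised, but the documents do not support that as a fact, because it depends on what enters the SUR. The reply does not dispose of the point. The protocol itself fixes scheme handling for the clinical outcomes, and itself describes an unrestricted mean per intervention as an input to the ICERs. Nothing in it requires scheme in the SUR.

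A second reply is that the effect may be small. Patient representatives did not expect randomisation to TURP to be a major barrier (section 2), and adjustment for baseline utility and service use could remove part of any bias. That is fair. A reader might also convert the equal-uptake share into pounds per man and compare it with the TURP equipment cost in section 2. That would need assumed uptake, an assumed utility gap and an assumed threshold, and the section 2 figure covers equipment and consumables only. No such sum is supported.

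A reader might extend the point to adverse events, since the safety population "Includes all randomised participants receiving a trial intervention" and so spans all schemes. The documents do not support that. Section 10.3.2 tabulates complications by treatment received and states no between-arm test. Transfusion, acute retention, catheter use, readmission and re-intervention are modelled with scheme as a fixed effect. A man from a no-TURP scheme who later received TURP would also be counted under TURP.

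**Conclusion.** The point holds for the economic analysis as written. Sections 10.3.5 and 10.3.6 set no scheme restriction and name no scheme term, while the same protocol treats all-scheme pooling of the primary clinical outcome as supplementary and in need of correction. Unless scheme enters the SUR, preference can confound the ICERs and CEACs, in both directions.

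The size is unknown. The share of each MIT arm from no-TURP schemes runs from 0% to 62.2% over the uptakes tried, with 48.5% only under equal uptake of all 11 schemes. These are shares of men, not biases. A bias also needs prognostic differences between men who accept and men who refuse a treatment, which the documents do not give. The version 6.0 entry in Appendix 1 records scheme pooling for sections 10.2, 10.3.1 and 10.3.2 but only historical controls for 10.3.5. That is consistent with an oversight, though it does not prove one.

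**What to change.** In section 10.3.6, state that:

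- incremental costs and QALYs are estimated with randomisation scheme as a fixed effect in both SUR equations;
- each MIT-versus-TURP increment uses the section 10.2 scheme sets, or, for the joint four-arm CEACs, all schemes with scheme fixed effects so that only within-scheme contrasts count;
- the bootstrap is stratified by scheme and arm.

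In section 10.3.5, label unadjusted all-scheme mean costs per intervention as descriptive.

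The change needs wording in the protocol and any health economics plan, with no new data or visits. It should be made before outcome data by arm are seen. Its cost is precision. Under equal uptake at N = 536, restriction leaves about 69 rather than 134 randomised men per arm per contrast, so standard errors rise by a factor of about √(134/69) = 1.39 before attrition. The all-scheme version limits this loss, but it assumes that treatment effects do not vary by scheme. Section 10.2 already expects over-recruitment to fill these same comparisons, and that would help the economic contrasts too.

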10.3.6. The Within Trial Analysis (WTA)

The base case within trial analysis will compare changes in health-related QoL, based on responses to the EQ-5D-5L at baseline, six weeks, six and 12 months. Responses to the EQ-5D-5L will be combined with a UK tariff that is relevant at the time the study reports and used to estimate QALYs. The results of the analyses will be presented as point estimates of mean incremental costs and QALYs. An adjusted analysis will be used to estimate the point estimates of the mean incremental costs, effects and cost-effectiveness using seemingly unrelated regression (SUR). We will explore the uncertainty in estimates of cost-effectiveness through a stochastic sensitivity analysis drawing bootstrapped samples of mean costs and mean QALYs. Results from this analysis will be combined willingness-to-pay (WTP) threshold values generating cost effectiveness acceptability curves (CEACs) that represent the probability of the interventions being cost-effective at each WTP value. As part of the CEA we will also estimate the distribution of costs and health benefits (QALY gains) by socio-economic status using IMD data.

Secondary analysis will be conducted and the cost-effectiveness analysis will be replicated at two and three years post-intervention.

10.3.7. Longer-Term Economic Model

Longer term model: The timeline of the trial may not capture all of the costs and health outcomes associated with the interventions. Hence, a decision model will also be developed to estimate costs and outcomes over the lifetime of the patient. The model will be developed in accordance with the NICE reference case (Methods for NICE technology appraisals). [35] Data from the trial will be the main source of data for this, but further data will be derived from the literature and clinical input. The economic model will be used to quantify the uncertainties facing decision-makers and to help inform decisions about the direction of future research. This will be explored using variants of value of information analysis. The results of these analyses will be presented as point estimates of mean incremental costs, and QALYs and incremental cost effectiveness ratios. The model will be consistent with good practice guidelines. [36] The data from the trial will be the main source of data for the model, but further data will be systematically derived from the literature and from expert clinical input. The model will be developed in accordance with the NICE reference case. We anticipate that the model will take the form of a Markov-type, state transition model although the

precise structure of the model will be developed during the project and will reflect the clinical decision question and the course of the condition.

